14.3.3 Laboratory Data Tables
Table 14.3.3.1.1 Hematology Results by Time Point (Safety Analysis Set)
Table 14.3.3.1.2 Biochemistry Results by Time Point (Safety Analysis Set)
Table 14.3.3.1.3 Coagulation Results by Time Point (Safety Analysis Set)
Table 14.3.3.2.1 Shift Summary of Hematology Results by Reference Range and Time Point (Safety Analysis Set)
Table 14.3.3.2.2 Shift Summary of Biochemistry Results by Reference Range and Time Point (Safety Analysis Set)
Table 14.3.3.2.3 Shift Summary of Coagulation Results by Reference Range and Time Point (Safety Analysis Set)
Table 14.3.4.1 Vital Sign Results by Time Point (Safety Analysis Set)

Figure 14.2.1.1 Fold Change from Baseline Serum SARS-CoV-2 RBD Antibodies (IgG) (Per Protocol Immunogenicity Set)
Figure 14.2.1.3 Fold Change from Baseline Serum SARS-CoV-2 neutralizing Antibodies MN 25 TCID50 (Per Protocol Immunogenicity Set)
Figure 14.2.2.1 Mean Fold Change from Baseline Serum SARS-CoV-2 RBD Antibodies (IgG) (Per Protocol Immunogenicity Set)
Figure 14.2.2.3 Mean Fold Change from Baseline Serum SARS-CoV-2 neutralizing Antibodies MN 25 TCID50 (Per Protocol Immunogenicity Set)
Figure 14.2.3.1 Individual Serum SARS-CoV-2 RBD Antibodies (IgG) (Per Protocol Immunogenicity Set)
Figure 14.2.3.3 Individual Serum SARS-CoV-2 neutralizing Antibodies MN 25 TCID50 (Per Protocol Immunogenicity Set)
Figure 14.2.4.1 Summary of Serum SARS-CoV-2 RBD Antibodies (IgG) (Per Protocol Immunogenicity Set)
Figure 14.2.4.3 Summary of Serum SARS-CoV-2 neutralizing Antibodies MN 25 TCID50 (Per Protocol Immunogenicity Set)
Figure 14.2.5.1 SARS-CoV-2 RBD Antibodies (IgG) by Time Point (Per Protocol Immunogenicity Set)
Figure 14.2.5.3 SARS-CoV-2 neutralizing Antibodies MN 25 TCID50 by Time Point (Per Protocol Immunogenicity Set)
Figure 14.3.1.1 Overview of Solicited Adverse Events with at Least One Intensity Grade 3 (Safety Analysis Set)
Figure 14.3.2.1 Hematology Results by Time Point (Safety Analysis Set)
Figure 14.3.2.2 Biochemistry Results by Time Point (Safety Analysis Set)
Figure 14.3.2.3 Coagulation Results by Time Point (Safety Analysis Set)
Listing
Listing 16.2.1.1 Discontinued Subjects (All Subjects)
Listing 16.2.1.2 Discontinuation of Investigational Product (IP) (Safety Analysis Set)
Listing 16.2.2 Protocol Deviations (All Subjects)
Listing 16.2.3.1 Subject Analysis Sets (All Subjects)
Listing 16.2.3.2 Subject Time Points (Safety Analysis Set)
Listing 16.2.3.3 Censoring (Safety Analysis Set)
Listing 16.2.4.1 Demographic and Baseline Data (Safety Analysis Set)
Listing 16.2.4.2 General Medical History (Safety Analysis Set)
Listing 16.2.4.3.1 Primary Co-Morbidities - Chronic Kidney Disease (Safety Analysis Set)
Listing 16.2.4.3.2 Primary Co-Morbidities – COPD (Safety Analysis Set)
Listing 16.2.4.3.3 Primary Co-Morbidities – Obesity (Safety Analysis Set)
Listing 16.2.4.3.4 Primary Co-Morbidities – Chronic Cardiovascular Disease (Safety Analysis Set)
Listing 16.2.4.3.5 Primary Co-Morbidities – Chronic HIV Infection (Safety Analysis Set)

Listing 16.2.4.3.6 Primary Co-Morbidities – Type 2 Diabetes Mellitus (Safety Analysis Set)
Listing 16.2.4.3.7 Primary Co-Morbidities – Subjects with a Renal Transplant (Safety Analysis Set)
Listing 16.2.4.4 Prior and Concomitant Medications (Safety Analysis Set)
Listing 16.2.4.5 Prior and Concomitant Vaccinations (Safety Analysis Set)
Listing 16.2.5.1 Administration of Investigational Product (Safety Analysis Set)
Listing 16.2.6.1 Vaccine-elicited IgG RBD Titers (Per Protocol Immunogenicity Set)
Listing 16.2.6.2 Vaccine-elicited IgG RBD Titers (Immunogenicity Set)
Listing 16.2.6.3 Virus Neutralizing Titers MN 25 TCID50 (Per Protocol Immunogenicity Set)
Listing 16.2.6.4 Virus Neutralizing Titers MN 25 TCID50 (Immunogenicity Set)
Listing 16.2.6.5 IgG NP Results (Immunogenicity Set)
Listing 16.2.6.7 Subjects with Virologically-Confirmed SARS-CoV2 infection as measured by RT-PCR (Safety Analysis Set)
Listing 16.2.6.8 Subjects with Asymptomatic SARS-CoV-2 Infection as measured with Retrospective Serology (Immunogenicity Set)
Listing 16.2.6.9 COVID-19 Symptoms (Safety Analysis Set)
Listing 16.2.7.1 Adverse Events (Safety Analysis Set)
Listing 16.2.7.2 Local Solicited Adverse Events (Safety Analysis Set)
Listing 16.2.7.3 Systemic Solicited Adverse Events (Safety Analysis Set)
Listing 16.2.7.4 Systemic Solicited Adverse Events 7 Days before Dose 1 (Safety Analysis Set)
Listing 16.2.7.5 Serious Adverse Events (Safety Analysis Set)
Listing 16.2.7.6 All Deaths (Safety Analysis Set)
Listing 16.2.8.1 Hematology Results and Change from Baseline (Safety Analysis Set)
Listing 16.2.8.2 Biochemistry Results and Change from Baseline (Safety Analysis Set)
Listing 16.2.8.3 Coagulation Results and Change from Baseline (Safety Analysis Set)
Listing 16.2.8.4 Pregnancy Test Results (Females of Childbearing Potential only) (Safety Analysis Set)
Listing 16.2.9 Vital Signs (Safety Analysis Set)
Listing 16.2.10 Electrocardiogram Results (Safety Analysis Set)
Listing 16.2.11 Physical Examinations (Safety Analysis Set)

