Safety laboratory values will be classified into low/normal/high based on laboratory normal ranges. Each parameter will be presented by descriptive statistics at each visit including change from baseline. Shift tables with normal ranges will be presented. All laboratory values will be listed. A separate listing for abnormal lab values will be presented.

Vital signs will be summarized by descriptive statistics at each visit including change from baseline and a listing will be provided.

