10.4 Case Definitions of Co-morbidities

Subjects with the following selected co-morbidities are at increased risk of severe illness from COVID-19 and will be included in the trial. Life expectancy of at least 1 year as per the Investigators' assessment is required for inclusion of the subject into the trial.

- **Chronic kidney disease:** Kidney function will be ascertained from the serum creatinine measurement within the last 6 months, converted into estimated glomerular filtration rate (eGFR) using the Chronic Kidney Disease Epidemiology Collaboration (CKD-EPI) equation, with impaired kidney function defined as eGFR <60 mL/min/1.73m².
 - Mild chronic kidney disease is defined as an eGFR between 60-89 mL/min/1.73 m².
 - Moderate chronic kidney disease is defined as an eGFR between 31-59 mL/min/1.73 m² with stable therapy and good maintenance over at least 6 months [1].
- **Chronic obstructive pulmonary disease (COPD)** (including emphysema and chronic bronchitis).
 - Mild COPD with or without cough or sputum production is defined as forced expiratory volume in 1 second/forced vital capacity (FEV₁/FVC) <0.7 and FEV₁ ≥80% predicted.
 - Moderate COPD with or without cough or sputum production is defined as FEV₁/FVC <0.7 and FEV₁ ≥50%, but <80% predicted with stable treatment (GOLD Criteria for COPD severity).
- **Obesity** with body mass index >32 kg/m².
- **Chronic cardiovascular disease** (heart failure, structural heart disorder, coronary artery disease, cardiomyopathies, arterial hypertension), including the following:
 - Heart failures (according to New York Heart Association [NYHA] classification [2]):
 - Class I: No limitation of physical activity. Ordinary physical activity does not cause undue fatigue, palpitation, dyspnea (shortness of breath).
 - Class II: Slight limitation of physical activity. Comfortable at rest. Ordinary physical activity results in fatigue, palpitation, dyspnea (shortness of breath).

- A structural heart disorder
 - without symptoms
 - with symptoms.
- Coronary artery disease:
 - Mild with metabolic equivalent threshold (MET)¹ <3, stable with medication.
 - Moderate with MET >3 – 5.9, stable with medication.
- Cardiomyopathies of non-infective and metabolic origin:
 - Mild with MET <3, stable with medication.
 - Moderate with MET >3 – 5.9, stable with medication.
- Hypertension (National Institute for Health and Care Excellence [NICE] categorization [4]):

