 - Stage 1 hypertension: Clinic blood pressure ranging from 140/90 mmHg to 159/99 mmHg and subsequent ambulatory blood pressure monitoring (ABPM) daytime average or home blood pressure monitoring (HBPM) average blood pressure ranging from 135/85 mmHg to 149/94 mmHg.
 - Stage 2 hypertension: Clinic blood pressure of 160/100 mmHg or higher but less than 180/120 mmHg and subsequent ABPM daytime average or HBPM average blood pressure of 150/95 mmHg or higher.
- **Chronic HIV infection with stable aviremia (<50 copies/mL) and CD4 count >350/mL** as documented by blood samples taken within 12 months before enrollment. Viral load <50 copies/mL over 12 months with transient changes of 50-350 copies/mL is allowed.
- **Type 2 diabetes mellitus**, controlled with medication [$\text{HbA1c} < 58 \text{ mmol/mol (7.45\%)}; [(\text{HbA1c} \text{ in \%} - 2.15) \times 10.929 = \text{HbA1c in mmol/mol}]$]
- **Subjects with a renal transplant** at least a year ago under stable conditions for at least 6 months with medications, categorized as low risk of rejection.

Following inclusion of 25 cases of mild to moderate conditions under chronic kidney disease, COPD, chronic cardiovascular disease and diabetes mellitus, more severe conditions can be included into the trial upon iSCR and DSMB Chair approval and subjected to the clinical Investigator's decision. Under cardiovascular disease, the following cases can be included:

- Heart failures (according to NYHA classification [2]) Class III: Marked limitation of physical activity. Comfortable at rest. Less than ordinary activity causes fatigue, palpitation, or dyspnea (shortness of breath).
- Coronary artery disease: Severe with MET >6, stable with medication.
- Cardiomyopathies of non-infective and metabolic origin: Severe with MET >6, stable with medication.

¹ MET is defined as the amount of oxygen consumed while sitting at rest and is equal to 3.5 mL O₂ per kg body weight/min and is roughly equivalent to the expenditure of 1 kcal per kilogram of body weight per hour; 1 MET is the rate of energy expenditure while at rest. A 4 MET activity expends 4 times the energy used by the body at rest. Light MET is <3, moderate is 3 to 5.9 and vigorous is ≥6.0. MET 1 can take care of him/herself and may not maintain themselves and gets constraints on exertion. MET 4 can climb a flight of stairs or walk up a hill and can participate in other strenuous activities; >2-3 METs is fit normal person with well controlled with medication [3].

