12.7.4 Laboratory Data

Blood samples for determination of hematology, clinical biochemistry and coagulation will be analyzed at each trial visit they are collected by co-morbidity for SAS. In case of abnormal results additional analyses will take place.

All laboratory data will be summarized in International System (SI) units. The conversion factors from conventional to SI units will be documented in the Local Lab Conventions document for this trial.

Laboratory data will be graded according with the United States Food and Drug Administration (FDA) toxicity grading scale [5].

All laboratory data will be listed.

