12.7.4.2 Chemistry

Clinical Chemistry/Biochemistry parameters include Sodium, Potassium, Urea Nitrogen (BUN), Urea, Creatinine, Calcium, Total Protein, Albumin, Bilirubin (Total), Direct Bilirubin, Indirect Bilirubin, Aspartate Aminotransferase (AST; SGOT), Alanine Aminotransferase (ALT; SGPT), Gamma Glutamyl Transferase (GGT), Lactate Dehydrogenase (LDH), Alkaline Phosphatase (ALP), Magnesium, C-Reactive Protein (CRP).

Chemistry parameters will be summarized (n, mean, SD, median, Q1, Q3, minimum and maximum), including change from baseline at each visit. In addition, shift tables summarizing the shift including baseline, minimum and maximum post-baseline values and last value will be presented. In addition, all parameters will be presented in a line plot for all planned visits.

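### The laboratory shift tables have no cell for further worsening from an already abnormal baseline, which matters mainly for creatinine and urea in the two renal strata, and the promised toxicity grades have no titled output

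*SAP*

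**What the plan says.** Protocol 10.3.5.1 sets the categories: "Safety laboratory values will be classified into low/normal/high based on laboratory normal ranges". It then adds: "Shift tables with normal ranges will be presented".

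SAP 12.7.4.2 says which chemistry values enter the shift: "shift tables summarizing the shift including baseline, minimum and maximum post-baseline values and last value will be presented". SAP 12.7.4.1 and 12.7.4.3 say the same for hematology and coagulation. None of the three names a category beyond the reference range. In Appendix 4, Tables 14.3.3.2.1 to 14.3.3.2.3 share one title pattern, for example "Shift Summary of Biochemistry Results by Reference Range and Time Point (Safety Analysis Set".

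SAP 12.7.4 also promises grading: "Laboratory data will be graded according with the United States Food and Drug Administration (FDA) toxicity grading scale". Protocol 9.1.3 makes the same promise. No laboratory table, figure or listing title in Appendix 4 mentions a grade.

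The case definitions in SAP 10.4 admit subjects with reduced renal function. One reads "Moderate chronic kidney disease is defined as an eGFR between 31-59 mL/min/1.73 m²", and more severe disease may follow once 25 mild to moderate cases have been reviewed. Renal transplant recipients form a separate stratum, with the transplant "at least a year ago under stable conditions for at least 6 months with medications, categorized as low risk of rejection". Creatinine, urea nitrogen and urea are all in the chemistry panel of SAP 12.7.4.2.

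**The concern.** A shift table by reference range works well when most subjects start within range. Here two of the seven strata are defined by renal disease or a transplanted kidney, and some of those subjects can be expected to have creatinine or urea above range on Day 1. For them, a further rise after vaccination does not change the category.

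Protocol 3.3.1 says the trial is meant to show whether subjects with co-morbidities carry extra risk from vaccination. Protocol 9.1.1 makes each subject his or her own control, and SAP 12.7 asks for results by co-morbidity. The natural summary for that purpose is a count, per stratum, of subjects who became worse than their own baseline. The planned shift tables cannot supply it for anyone who starts out of range.

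**Working it through.** No sample size, power or error-rate figure bears on this point, and the plan states no number to reproduce. The check is of what the categories can record.

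**Step 1: the cells.** Three baseline categories by three post-baseline categories give 3 × 3 = 9 cells. The row for a high baseline has three: high to low, high to normal, high to high. None stands for a further rise. Using the maximum post-baseline value does not help, because a maximum above a high baseline is still classed as high. The low row is the mirror image for a further fall.

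**Step 2: classifying assumed values.** Values are in multiples of the upper limit of normal (ULN), with an assumed lower limit of 0.6 × ULN. These figures are assumptions; the documents give no reference ranges. Each baseline is multiplied by 1.1, 1.25, 1.5, 2, 3 and 5.

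| Assumed baseline (× ULN) | Combinations | Change of category | No change |
|---|---|---|---|
| 1.1, 1.25, 1.5, 2, 3 (high) | 5 × 6 = 30 | 0 | 30 (high to high) |
| 0.7, 0.8, 0.9, 0.99 (normal) | 4 × 6 = 24 | 19 (normal to high) | 5 (normal to normal) |

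The same rises mostly register from a normal baseline and never from a high one. The five that stay normal do not exceed the upper limit.

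**Step 3: a sense of scale.** If creatinine is taken as inversely proportional to eGFR (a simplifying assumption, not the equation the protocol names), a fall across the whole moderate band, from 59 to 31, is a rise of 59/31 = 1.90-fold. If the value is above range throughout, that is one high to high entry. This illustrates the cell logic and does not estimate how often it would happen.

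**Step 4: what the other planned outputs offer.**

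| Output | Can it show further worsening? | Does it count subjects worsening from an abnormal baseline? |
|---|---|---|
| Tables 14.3.3.1.1–3, with change from baseline (SAP 12.7.4.1–3) | Yes, including through the maximum and minimum | No |
| Figures 14.3.2.1–3, line plots | Yes | No |
| Listings 16.2.8.1–3, results and change from baseline | Yes, subject by subject | No |
| Table 14.3.2.26.1 (AESIs) and the other adverse event tables | Yes, if the investigator reports an event | No |
| Tables 14.3.3.2.1–3, shift by reference range | Not from high upwards or from low downwards | No |

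**The case against.** A reader might infer that deterioration in renal subjects, even acute kidney injury, would pass through the report as no change. The documents do not support that. Acute kidney injury is on the AESI lists of both documents (Protocol Appendix 8, SAP Appendix 2), and AESIs are tabulated for the whole trial. Protocol Appendix 9 counts exacerbation of a pre-existing condition as an adverse event, and Protocol 9.1.5 says changes in the severity of underlying conditions will be monitored. The shift table is not the route by which such events are detected.

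Nor do the by-visit summaries conceal single subjects behind a mean. They report minimum and maximum and include change from baseline, by co-morbidity. On the natural reading, the largest individual rise at each visit is on the page. Listings give every subject's change, and SAP 6.3 puts the analysis at 129 subjects, so reading through them is practical. The table shells are a separate document (SAP 10.0), and SAP 12.0 says listings carry the relevant derived variables. A grade column may therefore exist even though no title names it.

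All of this stands and limits the consequence. Two things remain. A maximum shows how large the largest change was, not how many subjects worsened or whether they started out of range. The adverse event route also depends on judgment at just this point: Protocol 9.1.3 makes a laboratory abnormality an adverse event only if the investigator finds it clinically significant, and the laboratory example in Appendix 9 sets aside findings related to known concomitant disease. An objective count would add something the other outputs do not.

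**Conclusion.** The point holds as a minor presentational gap. The only planned laboratory shift tables cannot register a further rise from high or a further fall from low. No other planned table counts such subjects, and the promised grading has no titled laboratory output.

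Three wider readings should be avoided.

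- The problem is not general to the trial population. Obesity, HIV infection and hypertension are not defined by an abnormal value on this laboratory panel, and SAP 10.4 includes mild kidney disease with eGFR 60–89. It concerns mainly creatinine and urea in the chronic kidney disease and renal transplant strata.
- A high baseline cannot always be said to look only stable or improved. High to low is a possible cell and may be adverse for some analytes. What is missing is a cell for higher still.
- No share of affected subjects can be given. The documents do not report how many renal subjects were enrolled or how many started out of range. Safety laboratory tests were limited to at most 50 subjects per co-morbidity.

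The conclusion assumes that the shells follow the Appendix 4 titles and the categories in Protocol 10.3.5.1. If they already show grade shifts, the gap is only that the SAP does not say so.

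**What to change.** Keep Tables 14.3.3.2.1–3 as they are and add two outputs to SAP 12.7.4 and Appendix 4:

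1. For parameters the FDA scale covers, a table of baseline grade by worst post-baseline grade, by co-morbidity and overall.
2. For creatinine in the chronic kidney disease and renal transplant strata, the number of subjects by maximum post-baseline ratio to their own baseline. The sponsor should choose the categories and fix them before database lock. They serve reporting only and are not thresholds for clinical action.

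The second is needed because the first has its own ceiling. The SAP's reference list shows that the scale was written for healthy volunteers, so many renal subjects may have a grade above zero at baseline, and one already in the top grade cannot move higher.

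The cost is some SAP wording and extra programming on data already planned for collection and grading already promised. No new samples or visits are required. With small strata the counts will be low and should be read descriptively, as SAP 12.0 intends for the whole analysis.
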